1.2.4 Theoretical Risks and Benefits

There is a theoretical risk of thyroid dysfunction because the active ingredient is sodium iodide. Gastrointestinal irritation and bleeding were seen at 40mg/kg per day in 7-day dosing toxicology studies in dogs. The dose at which no adverse effects were seen was at 20mg/kg per day in 7-day dosing (the intended clinical doses are 1 or 2 mg/kg per day). Faraday continues to actively assess and closely monitor these potential risks in clinical trial subjects.

Trauma patients in ICU are at high risk of developing muscle weakness and other organ failures consequent at least in part to a systemic inflammatory response. This leads to short and long-term morbidity and poor outcomes and has in part been characterized as a "post ICU syndrome." This represents a very high unmet medical need for which effective and safe interventions would be of huge benefit. Subjects randomized to FDY-5301 are anticipated to have potential benefits such as improvement in muscle wasting or other organ dysfunction consequent on serious injury. Subjects randomized to placebo are not anticipated to have any adverse effects related to the administration of intravenous sterile saline. In addition, FDY-5301 or placebo will be administrated in addition to standard of care, so no subject in FDY-5301 clinical studies will have any approved treatment withheld. Subjects randomized to FDY-5301 will have the prospect of benefit from this adjunctive experimental medication.

1.3 Rationale for Disease Indication

The precise mechanism by which intensive care unit acquired weakness (ICUAW) occurs is unclear; however, there is mounting evidence to suggest that organ and muscle tissue injury are mediated at least in part by reactive oxygen species (ROS) (Abrigo 2018, Dodd 2010, Li 2008) and systemic inflammation (Friedrich 2015). Faraday has demonstrated, through a series of nonclinical mechanistic and pharmacologic studies, the ability of FDY-5301 to catalytically disproportionate hydrogen peroxide, reduce inflammation, improve survival, attenuate tissue injury, and, in particular, reduce muscle injury in trauma and cancer animal models.

The hypothesis, therefore, is that damage consequent to the systemic inflammatory response from a major injury will be attenuated by the administration of an exogenous reducing agent (iodide). This will be measurable as diminished tissue injury, including skeletal muscle, in ICU survivors.

Confidential Page 19 of 64

Importantly, iodide is a catalytic disproportionator of peroxide, which differentiates it from vitamins C and E, and other "antioxidants" which, unlike iodide, are oxidized in such reactions into pro-oxidant metabolites. In addition, iodide, as FDY-5301, can be quickly, easily and safely introduced into patients at doses that are potently catalytic of ROS, and are thousands of fold higher than physiological levels of endogenous iodide.

Given the apparent roles that oxidative stress and oxidant-mediated tissue injury may play in the development of multiple organ failure, including muscle wasting, immediate supplementation with a potent reducing agent such as iodide may augment patients' endogenous defenses and serve to prevent the development of organ dysfunction (Schorah 1996, Hemila 1997, Maderazo 1991).

This hypothesis is supported by recent data from a phase 2 STEMI study in ST elevation myocardial infarction patients, which suggests that FDY-5301 may have an effect in reducing myocardial ischemia-reperfusion injury after a single IV bolus dose. The improvement of infarct size and cardiac function seen, in particular at the 2.0 mg/kg dose, suggests that FDY-5301 might be expected to confer benefit in the oxidative damage due to the prolonged inflammatory response to major injury.

The cumulative human and preclinical experience to date suggest that FDY-5301 has an acceptable safety profile, and a broad therapeutic margin.

1.4 Rationale for Study Design

The study is designed as a randomized double-blind parallel-group comparison of FDY-5301 and placebo. This construct is regarded as the gold standard assay for assessing drug efficacy and safety, in that it mitigates observer and reporter bias, has a control group, and should allocate similar populations to each group. Given the potential heterogeneity of the major trauma ICU population, inclusion and exclusion criteria have been designed to ensure a degree of homogeneity, especially in terms of conditions that could compromise efficacy measures, e.g., head injury and bilateral lower limb fractures. To ensure equal representation in each group, the randomization will be stratified by the presence or absence of any pelvic or lower limb fracture.

Outcome measures have been selected to collect information on the anatomical, biochemical, and functional effects on muscle and on multiple organ failures. In addition, composite rating scales are employed to identify effects on specific domains of musculoskeletal and organ function.

The co-primary outcomes are the Chelsea Critical Care Physical Assessment Tool (CPAx) and organ dysfunction total time to recovery (TTR). CPAx is a tool used to measure functional status relevant to ICU patients and is dependent on muscle strength and coordination. CPAx will provide useful information as to whether muscle wasting and its consequences on muscle function can be mitigated by FDY-5301. Organ dysfunction total TTR will provide important data on the clinical progress of patients with respect to the cluster of organ failures often seen in these patients as a consequence of their injuries and systemic inflammatory responses.

Confidential Page 20 of 64

1.5 Justification for Dose

The selected dosing regimen for FDY-5301 is 1 or 2 mg/kg daily for 7 days and is based on the available safety, efficacy and PK modeling data for FDY-5301.

FDY-5301 is expected to provide clinically significant exogenous reducing capacity when administered to major trauma ICU patients. The systemic inflammatory response which triggers a catabolic state occurs very early following major trauma, but is postulated to last for longer than a day, and perhaps weeks following trauma (Pedroso 2012). For this reason, and given the poor outcomes expected in the ICUAW population, 7-day dosing is proposed to provide reducing capacity for a period long enough to potentially confer clinical benefit. Daily dosing is based on the half-life of FDY-5301 in healthy volunteers of 6 to 8 hours, implying a return to baseline levels after 24 hours.

Up to 10 mg/kg IV of FDY-5301 has been given to healthy volunteers in a phase 1 study without adverse effects, and a single IV bolus dose of 2 mg/kg was well tolerated in the phase 2 AMI reperfusion study in acutely ill subjects. Specifically, thyroid function tests showed similar group means across all groups, with no suggestion of a drug effect. In a published study of healthy volunteers, cumulative doses of 14 mg/kg of sodium iodide (given as daily oral doses of 1 mg/kg for 14 days) were well tolerated. (Robison 1998).

In nonclinical safety testing, the NOAEL in a rat 14-day repeat dose GLP toxicity study was 74 mg/kg/day and the NOAEL in a GLP dog 7-day repeat dose study was 20 mg/kg/day. These data support daily dosing in subjects at the high dose in this study of 2 mg/kg for up to 7 days.

The PK profile of FDY-5301 has been well characterized in humans. Following IV administration, a rapid maximal concentration (C_{max}) occurs, followed by rapid initial clearance from plasma, a terminal half-life of 6 to 8 hours, and trough levels approaching zero at 24 hours. Exposure will be adequate for daily administration without accumulation, even in subjects with renal impairment.

Confidential Page 21 of 64

2 TRIAL OBJECTIVES AND ENDPOINTS

The purpose of the trial is to evaluate the efficacy, safety, and PK of FDY-5301 compared to placebo in major trauma ICU patients at risk of ICUAW.

Objectives	Endpoints								
Primary	Coprimary								
To assess the effect of FDY-5301 on muscle function and organ dysfunction in the major trauma ICU population	 Chelsea Critical Care Physical Assessment Tool (CPAx) total score at Day 10, or hospital discharge, whichever occurs first Organ dysfunction total time to recovery (TTR) until Day 28 								
Secondary	Secondary								
To assess the effects of FDY-5301 on other clinical outcomes in the major trauma ICU population	The secondary endpoints will be analyzed in the following sequence: • Medical Research Council Sum Score (MRC-SS) at Day 28 or hospital discharge, whichever occurs first • Worst Sequential Organ Failure Assessment (SOFA) score during ICU stay • Overall Survival at Day 28								
Safety	Safety								
To investigate the safety and tolerability of up to 7 daily bolus IV doses of FDY-5301 in the major trauma ICU population	Safety will be evaluated based on occurrence of or changes throughout the study in the following parameters: • Adverse events (AEs), treatment-emergent adverse events (TEAEs) and serious adverse events (SAEs) • Clinical laboratory assessments (hematology, clinical chemistry, and thyroid function tests) • 12-lead electrocardiogram (ECG) assessments								
Exploratory	Exploratory								
To assess the effects of FDY-5301 on skeletal muscle, muscle function, and other clinical outcomes and to investigate the PK of up to 7 daily bolus IV doses in the major trauma ICU population	 Overall survival at Month 3 and Month 6 from date of injury Time to successful ventilator extubation from time of first dose Time to hospital discharge from first hospital arrival time and time of first dose, and discharge disposition (e.g., home, home with community support, rehabilitation unit, or nursing home) 								

Confidential Page 22 of 64

- Incidence of sepsis through Day 28
- SOFA score and sub score components at Days 1, 3, 7, 14, 21, and Day 28 or ICU discharge, whichever occurs first
- CPAx total score and sub score components at Days 1, 3, 7, 10 (sub score components only), 14, 21, and Day 28 or hospital discharge, whichever occurs first
- Medical Outcomes Study Questionnaire Short Form 36v2 Health Survey (SF-36v2) and activities of daily living questionnaire (Barthel Index) at Day 28 or hospital discharge (whichever occurs first), Month 3, and Month 6
- Proportion of subjects who can complete any sit-tostand maneuver and the number of sit-to-stand maneuvers completed in 30 seconds at Days 10, 14, 21, and Day 28 or hospital discharge, whichever occurs first
- Individual organ dysfunction TTR until Day 28

In a subset of subjects:

- Blood metabolic, inflammatory, and biochemical markers of muscle damage analysis at Days 1, 3, and 7
- Plasma iodide concentrations evaluated up to 4 hrs pre- and post-dose on Days 1, 3, and 7
- Leukocyte gene expression analysis at Days 1 and 7
- Percent change from baseline in the level of the 3rd lumbar (L3) vertebra Skeletal Muscle Index (SMI) and other muscle volume measures based on Computerized Tomography (CT) scan at Day 10

[figure not shown]
Confidential Page 23 of 64

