10.2.2 Handling of Missing Data

CPAx total scores will be analyzed using ANCOVA on observed data. To assess the impact of missing data, multiple imputation will used as supplementary analysis. Tipping-point analysis will also be performed. Details will be described in the SAP.

For organ dysfunction total TTR, no imputation will be performed. For all other endpoints, missing observations will be excluded from analysis.

Descriptive summaries of efficacy and safety measures will be based on observed data.

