10.2.4 Efficacy Analyses

The ITT Population will be used for all efficacy analyses. The PP Population will be used as a sensitivity analysis to assess robustness of the efficacy results.

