10.2.4.3 Exploratory Efficacy Analyses

Continuous variables will be summarized by descriptive statistics (n, mean, median, standard deviation, minimum, and maximum) by treatment group. Continuous variables will also be analyzed using analysis of covariance or analysis of variance. The least-squares means, standard errors, and the 2-tailed 95% confidence intervals for the treatment group and placebo group will be presented.

Categorical variables will be summarized by frequency and percentage by treatment groups. Categorical variables will be analyzed using a Pearson's Chi-square test or Cochran-Mantel-Haenszel test.

Time to event data will be analyzed using Kaplan-Meier lifetables and a log-rank test to compare time to efficacy between treatment groups and placebo groups.

Confidential Page 48 of 64

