10.2.7 Sample Size Determination and Power Calculations

Approximately 252 subjects will be randomized in a 1:1:1 ratio to receive either FDY-5301 1 mg/kg, FDY-5301 2 mg/kg, or placebo (i.e. 84 subjects per group).

With 252 subjects (with a drop-out rate of 15%, corresponding to 213 evaluable subjects), using a 2-sided significance level of 0.05 and placebo group mean in CPAx total score at Day 10 of 30, assuming a standard deviation of 12 (Corner 2015 and Raymond 2020), this would provide >90% power if there exists an improvement of 6 points in the CPAx total score in the pooled treatment group (either FDY-5301 1mg/kg or 2 mg/kg) compared with placebo group, (i.e. scores of 36 for FDY-5301 vs. 30 Placebo).

Given the assumption that median expected organ dysfunction recovery time is 7 days for the placebo group and the median expected organ dysfunction recovery time is 4.9 days for the pooled treatment group (Xiao 2011), i.e. an expected relative risk reduction of 30% and a 2-sided log-rank test at a significance level of 0.05, the study would have approximately 70% power if at least 213 events are observed (based on no subject being censored until Day 28).

Confidential Page 49 of 64

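### By-day SOFA stops at ICU discharge and absent values are excluded, so the Day 7, 14 and 21 treatment comparisons cover only subjects still in ICU, not the randomised groups

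*Combined protocol and SAP*

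**What the plan says.** Section 2 lists as an exploratory endpoint the "SOFA score and sub score components at Days 1, 3, 7, 14, 21, and Day 28 or ICU discharge, whichever occurs first". In section 5, Table 1, footnote i to the SOFA row says that SOFA is collected only until ICU discharge, even if the subject stays in hospital. Footnotes a and b bring the final assessments forward for hospital discharge. No footnote schedules a SOFA at ICU discharge.

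Section 10.2.2 plans multiple imputation and a tipping-point analysis for CPAx only and no imputation for total organ dysfunction time to recovery (TTR). It then says: "For all other endpoints, missing observations will be excluded from analysis". For exploratory endpoints, section 10.2.4.3 says: "Continuous variables will also be analyzed using analysis of covariance or analysis of variance", with least-squares means, standard errors and 95% confidence intervals. Section 10.2.4 says: "The ITT Population will be used for all efficacy analyses".

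No section gives a SOFA value, rank or category to a subject who has left ICU or died before a scheduled day.

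The Day 10 CT scan (Table 1 footnote h and section 6.1.1) is done only in subjects still in hospital who had a standard-of-care abdominal CT around admission.

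**The concern.** Whether a subject is in ICU on Day 7, 14 or 21 is decided after randomisation and depends on organ function, which is what SOFA measures and what the primary objective expects the drug to improve. If the drug works, more active subjects leave early, and the exclusion rule drops them. Those left in the active arm are then, on average, slower to recover than those left on placebo. The intent-to-treat label does not repair this, because the exclusion rule reduces that population to subjects with a score on the day.

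The output would still be a least-squares mean difference with a confidence interval, set beside results that do compare the randomised arms. A reader could take a small or null difference as lack of effect on organ function. Deaths also remove subjects with no rule, which can push the result either way.

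**Working it through.** **The plan's own figure.** The protocol gives no SD, effect or power for by-day SOFA. The nearest stated figure is the power of the TTR log-rank test (section 10.2.7): medians 7 and 4.9 days, 213 events, two-sided 0.05, about 70%. With one third of subjects on placebo and hazard ratio 4.9/7 = 0.70:

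- power = Φ(√(213 × 1/3 × 2/3) × |ln 0.70| − 1.96) = Φ(6.880 × 0.3567 − 1.96) = Φ(0.494) = 0.689, which agrees.

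**Who might remain (proxy).** The documents give no ICU stay figures. Assume that ICU stay follows the organ-recovery medians and is exponential, so the share remaining is 2^(−day/median). The 1:1:1 allocation of 252 gives 84 placebo and 168 pooled active.

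| Day | Placebo share | Active share | Placebo n | Active n |
|---|---|---|---|---|
| 7 | 50% | 37% | 42 | 62 |
| 14 | 25% | 14% | 21 | 23 |
| 21 | 12.5% | 5.1% | 10–11 | 9 |

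**Simulation A (all parameters assumed).** 400,000 subjects per arm; baseline SOFA normal with mean 9 and SD 3, floored at 0; exponential decline with rate ln(3)/7 per day for the median subject (9 to 3 by Day 7); log-normal rate, SD 0.6 on the log scale; out of ICU once SOFA is 3 or less; no deaths. About 45% of placebo and 26% of active subjects are in ICU at Day 7 under the uniform benefit. Day 7 differences, active minus placebo:

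| Form of benefit | True, all subjects | Remainers, raw or ANOVA | Remainers, ANCOVA on baseline |
|---|---|---|---|
| Rate × 1/0.7 in everyone | -0.95 | -0.35 | -0.44 |
| Rate × 2 in the half with baseline ≤ 9 | -0.63 | +0.26 | -0.05 |

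In the first row ANCOVA loses 1 − 0.44/0.95 = 54% of the effect. In the second row selection runs through baseline severity, so the covariate removes the sign change but does not recover the effect. If the rate is instead doubled in the half who recover faster, a true -0.64 appears as +0.30 in ANCOVA.

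**Simulation B (a second assumed model).** 600,000 subjects, 1:2; linear decline, median rate 0.45 points per day, log-normal SD 0.8; out of ICU on the first day with SOFA ≤ 2 or ≤ 4; ANCOVA on Day 1 SOFA.

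- No drug effect: the remainers difference is about 0.
- Rate × 1.43 in everyone: a true -1.00 at Day 7 appears as -0.69 or -0.55, and a true -1.05 at Day 14 as -0.59 or -0.46.
- Benefit only in faster recoverers: a true -1.03 at Day 14 appears as +0.73 or +0.67.

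**Check of an obvious remedy.** Carrying the ICU-discharge SOFA forward in simulation A (uniform benefit) gives -0.45 at Day 7 against a true -0.95, and -0.11 at Day 14 against a true -0.60. Everyone discharged is held near the discharge threshold, so the effect is floored.

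**The case against.** The strongest reply is that little depends on this endpoint. It is exploratory and outside the sequential testing. Organ dysfunction is carried by total TTR as a co-primary, by the secondary "Worst Sequential Organ Failure Assessment (SOFA) score during ICU stay" with one value per subject, by Day 28 survival, and by individual-organ TTR. None of these conditions on being in ICU on a fixed day. This stands, and it sets the severity.

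The reply also notes that detail is deferred to a separate SAP (section 10) and, for SOFA scoring, to the Study Reference Manual (section 6.1.4). That has less force: the exclusion rule and the model are already fixed in the protocol, and no other rule for this endpoint appears in the documents.

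A reader might infer more than the documents support:

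- **That the planned ANCOVA would generally reverse a benefit.** Attenuation is the more robust result. The +0.26 comes from raw means or ANOVA, which section 10.2.4.3 permits as an option. Under ANCOVA the sign changed only when faster recoverers had the benefit.
- **That the 7 and 4.9 day medians describe ICU stay.** They are recovery times across five organ systems and serve only as a proxy. Simulation A's 45% and 26% at Day 7 differ from the proxy's 50% and 37%.
- **That the Day 10 CT result is biased against the drug.** It is selected on hospital stay, and no figure in the documents sizes that or gives its direction.

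**Conclusion.** The concern holds in limited form. As written, the Day 7, 14 and 21 SOFA comparisons are not comparisons of the randomised groups. That follows from the stated rules and needs no simulation. Day 1 is essentially unaffected and Day 3 little affected. The last time point, if read as a discharge-day score for those who leave early, mixes scores from different days, which is a related but separate difficulty.

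The size rests on assumed SOFA trajectories and discharge thresholds. With a uniform benefit, ANCOVA loses roughly half the Day 7 effect in simulation A, and 31% (threshold 2) or 45% (threshold 4) in simulation B. Other patterns of benefit can erase or reverse the effect, subject to the conditions above. Both models omit deaths, whose effect could go either way. The severity is minor: no confirmatory conclusion is touched.

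**What to change.** 1. Present in-ICU SOFA and its components at Days 7, 14 and 21 descriptively. Beside each mean, give the numbers per arm in ICU, discharged alive from ICU, and dead. Drop the least-squares-mean treatment comparison at these days.
2. If a between-arm comparison by day is wanted, include every randomised subject in a prespecified order (death worst, then in-ICU subjects by SOFA, discharged alive best) and use a rank-based test. As sensitivity analyses, set SOFA for those discharged alive to 0, and then to the ICU-discharge value. Carry-forward should not be the main analysis, because it floors the effect.
3. Add to Table 1 the SOFA at ICU discharge that the endpoint already names, taken from chart data.
4. For the Day 10 CT comparison, report the number of scans and the reason for each missing one, per arm, with no claim about the direction of bias.

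The cost is analysis-plan wording and one chart-based score per subject, which must be set up prospectively. The downside is that the ranking is a convention and gives no estimate in SOFA points. No treatment, eligibility or confirmatory test changes.

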3 INVESTIGATIONAL PLAN

3.1 Overall Study Design

This is a phase 2, randomized, double-blind, parallel-group, placebo-controlled, multicenter study of intravenous FDY-5301 in major trauma patients at risk of ICUAW. A summary of the study design is presented in Figure 1.

Figure 1: Study Schema

Key aspects of the study design include:

- Approximately 252 subjects will be randomized (1:1:1) to receive up to 7 daily bolus IV
 doses of FDY-5301 at 1 mg/kg or 2 mg/kg, or volume-matched placebo. To ensure equal
 representation in each group, the randomization will be stratified by the presence or absence
 of any pelvic or lower limb fractures.
- Randomized subjects will begin daily dosing with investigational product (IP) as soon as
 possible and within 48 hours of first hospital arrival time (i.e. in case of transfers, use time of
 arrival to first hospital immediately post injury), before any diagnosis of ICUAW has been
 made.
- IP will be administered in addition to standard of care; no standard treatment normally used
 in this population will be withheld as part of this study.
- All subjects will be followed in-hospital until Day 28 or discharge, whichever occurs first, at Day 28 if discharged earlier, and then by telephone visits at Month 3 and Month 6.

Confidential Page 24 of 64

3.2 Number of Centers/Subjects

This study will be conducted at approximately 12 centers globally. Approximately 252 subjects are planned for enrollment in this study.

3.3 Estimated Study Duration

Each subject's participation will be approximately 6 months from the time of screening to study exit.

